2.4.3 Block randomization

We will utilize a permuted block randomization scheme with a randomly varying block size (within each study site) to protect the integrity of the assignment masking.³ Any particular block size will be unknown to the study investigators. We will choose randomly varying block sizes, picking a block of size 4 with probability 2/3 and a block of size 6 with probability 1/3. Individuals have a higher probability of being in a block of size 6 because the blocks are larger. Many other choices would serve equally well. Given the block size, a random permutation of assignment orders will be generated.

2.4.4 Unique patient identifiers

Unique patient identifiers will be generated as follows. The first character will be a number:

The next character is a checksum character, which will be a single letter. The last three characters will be sequential digits beginning at 001. An example identifier is 4J101; all identifiers have exactly five characters, and no other study uses this format.

2.4.5 Random number generation

The choice of a random number seed determines the specific sequence of random numbers that will be produced by the random number generator. Once the seed is determined, the randomization assignments for all sites are determined. Details are given in the Appendix.

2.4.6 Provision of randomization list

Everyone to whom the randomization list should be provided (for each of the four sites) will receive it in the following format: a Microsoft Excel® spreadsheet containing the following columns: (1) the unique study identifier assigned to the patient (see Section 2.4.4), (2) an empty field into which the date of randomization may be entered (relevant only for the hospital/clinic staff holding the randomization lists), (3) the study drug assignment, written out in full as

Mycophenolate or Methotrexate. As discussed in Section 2.4.2, these lists will be treated confidentially.

Update: As of 18 January 2017, all randomization lists are electronic on REDCap. Once a patient is enrolled, the study coordinator logs the patient in the database and the system reveals the drug assignment, written out in full.

2.4.7 Quality assurance

Three quality assurance steps for the randomization list preparation are conducted. First, the software will have been tested during previous studies [REDACTED]. Second, the software that generates the assignments verifies approximate balance of subjects in each group before writing the Microsoft Excel® files. Each file will contain the study site as the first line. Finally, the output files will be visually inspected. The software and procedures have already been developed and successfully used in previous studies.

2.5 Masking

The clinical examiners, refractionists, OCT technicians, fundus photographers and fundus graders will be masked to the treatment assignment. Note that only the individuals listed in Section 2.4.8 will have copies of the randomization list. Full details of procedures to maintain masking as well as for potential unmasking in the event it becomes necessary for safety reasons are provided in the Manual of Operations. Principal Investigator [REDACTED] is masked.

3 Statistical Considerations

3.1 Baseline characteristics

At baseline, each eye (1) may be fully able to be assessed, (2) it may be possible assess part of the eye, but not be possible to assess the entire eye, or (3) it may not be possible to assess any of the eye. For each eye for which some assessment is possible, either (1) the eye shows no signs of uveitis, or the eye may show some signs of uveitis, but fail to meet the severity criteria (1+ anterior chamber cells, vitreous haze or no active retinal/choroidal lesions, as defined in the Manual of Operations), or (2) the eye meets the severity criteria as defined in the manual of operations. Some patients are monocular at baseline, one eye being either absent, or exhibiting such disease as to preclude the possibility of ever assessing the eye (i.e. phthisis).

For this trial, we summarize the above possibilities as follows. Each eye (OD or OS) may be classified into one of the following types at baseline:

- A. Eye fully assessible, does not meet the severity criteria as defined in the MOP
- B. Eye partially assessible, does not meet the severity uveitis criteria in the assessible region
- C. Eye fully assessible, meets severity criteria
- D. Eye partially assessible, meets severity criteria in assessible region
- E. Eye absent or too diseased to ever assess

Patients, not eyes, are the unit of assignment and of randomization. Thus, there are twenty-five possible types of patients. A patient is required to have at least one eye which meets severity criteria for uveitis, and which can be completely assessed. Eligibility is summarized in the following table; cells indicate the possibility of enrollment for a patient whose right eye classification corresponds to the row and whose left eye classification corresponds to the column (A-E being defined in the previous paragraph).

	OS: A	OS: B	OS: C	OS: D	OS: E
OD: A	Not eligible	Not eligible	Eligible	Not eligible	Not eligible
OD: B	Not eligible	Not eligible	Eligible	Not eligible	Not eligible
OD: C	Eligible	Eligible	Eligible	Eligible	Eligible
OD: D	Not eligible	Not eligible	Eligible	Not eligible	Not eligible
OD: E	Not eligible	Not eligible	Eligible	Not eligible	Not eligible

Assessment and follow-up depends on the status of the eye. Eyes classified as type E above are recorded as such at baseline, and never provide eye outcome related data. Because (a) inability to assess parts of the eye could be related to the progression of disease, but (b) inability to assess in the absence of signs of disease cannot be considered evidence of treatment failure, we use the following table to summarize how success at six months will be scored. In this table, the row corresponds to the status of an eye at baseline, and the column to the status of the eye considering the primary outcome of success at six months.

	Month 6: A	Month 6: B	Month 6: C	Month 6: D	Month 6: E
Baseline: A	Success	See below**	Fail	Fail	Fail*
Baseline: B	Success	See below**	Fail	Fail	Fail*
Baseline: C	Success	See below**	Fail	Fail	Fail*
Baseline: D	Success	See below**	Fail	Fail	Fail*
Baseline: E	NA	NA	NA	NA	NA

Specifically, note that an eye which is fully assessable at six months and which does not meet the specific criteria for failure of control is always considered a success. Eyes which are fully or partially assessable and which meet any of the criteria for failure are always considered to have failed. However, eyes which are only partially assessable but which meet no criteria in the assessable region may be scored successes or failures depending on their baseline status (see next paragraphs below). Eyes which were present at baseline but which are missing at the end of the study are listed as Fail* in the table; we propose to consider such eyes to have failed unless a specific reason demonstrates that the loss of the eye was completely unrelated to the presence or progression of disease.

The primary analysis is at the patient level. Both eyes must meet the success criteria for the patient to be considered a success.

****Incompletely assessable eyes.** Uveitis assessment for this purpose is based on (i) assessment of anterior cells, (ii) vitreous haze, and (iii) retinal or choroidal lesions. In the pilot study, (iv) assessment of vitreous cells was also used. We will have longitudinal measurements of inflammation according to the following schedule: anterior chamber cells, vitreous haze and

active retinal/choroidal lesions will be measured at Baseline, Week 2, Month 1 and every subsequent 4 weeks until the 6 month assessment (Phase I or Phase II) or 9 and 12 month assessment (Phase I 6-12 months).

Each of these (including the binary assessment of the presence of retinal or choroidal lesions) may be considered an ordinal variable, with relevant threshold values for each (used in determining eligibility for enrollment, or success in therapy).

Scoring of incompletely assessable eyes is governed by the following guiding principles:

1. In some patients, the front of the eye may be assessable, but the back of the eye cannot be examined and assessed clinically (even though the patient can still see out of the eye).
2. Worsening of uveitis may render it harder to assess the back of the eye, so that information cannot be considered missing at random in general.
3. Many uveitis patients have at least one eye which cannot be fully assessed, because of the progression of the disease itself. Excluding such patients or eyes completely is undesirable.
4. Treatment of uveitis will not reverse the damage which makes it difficult to assess all parts of the eye.
5. Worsening of cataracts may also cause an eye to become incompletely assessable, so that a change in assessability status does not always indicate a worsening of uveitis or a failure of uveitis treatment.

We chose the following simple, but conservative, approach to scoring such eyes. For an incompletely assessable field (anterior cells, vitreous haze, or presence of retinal or choroidal lesions) at any time, the worst value seen until that time will be assigned for the unavailable measurement. Thus, a decreasing ability to assess regions of the eye—in the absence of evidence of inflammation or uveitis criteria—does not imply failure of therapy. Decreasing ability to assess eyes which had signs of uveitis will imply failure of therapy. It is understood that this procedure will misclassify some events such as: (i) an eye which had vitreous haze or a retinal or choroidal lesion at baseline, which resolved over the course of the six months, and for which a progressing cataract rendered the posterior of the eye impossible to assess, will be scored as a failure, or (ii) an eye for which the posterior region had no inflammation at baseline, which then became impossible to assess, and then which develops posterior inflammation which cannot be seen, will be scored as a success. We believe such misclassifications will be infrequent.

Selected secondary outcomes, including vision, macular edema, time to control of inflammation, will be analyzed at the eye level. All eyes that meet inclusion criteria of inflammation at baseline will be included in this analysis. Linear or generalized linear mixed modeling will be conducted (see below for details).

The following is a brief summary of general guiding principles.

- For the primary outcome, if any portion of the eye cannot be assessed at baseline, and it *still cannot be assessed at Visit 6 or Visit 12*, if all other markers of success are met, this portion of the eye would be considered to have had successful therapy.
- For the primary outcome, if any portion of the cannot be assessed *by Visit 6 or 12* and this

same portion of the eye was *completely assessable* at baseline, if all other markers of success are met, then the last worst observation for this eye would be carried forward and used at the assessment of this eye portion.

- For the primary outcome, if an eye *becomes missing by Visit 6 or 12*, and it is related to uveitis (regardless of its disease status at baseline) if all other markers of success are met, this patient should be considered a failure.

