2.5.2. Treatment failure

- Failure due to efficacy:** Patients can be declared a treatment failure due to futility and be declared a treatment failure and enter Phase II **at any time during follow-up** if the following occurs: The treating physician determines that it is futile to continue the current study medication due to persistent, uncontrolled inflammation that appears to be non-responsive to treatment. This option of declaring futility should only be declared if treatment with study medication seems completely unlikely to be able to control inflammation. Since the medications take up to a few months to fully take effect, increase in inflammation early on in the trial is not an indication of treatment failure. Corticosteroids may be increased in the case of increased inflammation.

Efficacy will be judged at the primary endpoint of 6 months. Specifically, at 6 months, if there is a lack of efficacy, patients will be declared a treatment failure and enter Phase II if the following occurs: The patient does not have controlled inflammation (see Table 2) with a prednisone dose of 7.5 mg/day and less than or equal to 2 prednisolone acetate 1% drops per day by 6 months.

- Failure due to intolerance:** Patients who experience severe symptoms thought to be related to the drug should try a dose reduction if they are willing. If this is not successful and the patient is unable to continue their

medication due to symptoms and is also not willing to continue, treatment failure can be declared. Please refer to Table 5 for dose reduction guidelines. Trial of a dose reduction is strongly encouraged, however it **is not required** for a patient to be determined a treatment failure due to intolerability.

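### SAP 3.1 scores one narrow primary-endpoint trajectory two ways: a region unreadable at baseline and month 6 but graded inflamed in between fails under the detailed rule and succeeds under the summary bullet

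*Combined protocol and SAP*

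**What the plan says.** SAP 3.1 classes each eye by whether it can be assessed and whether it meets the severity criteria. Its month-6 scoring table leaves one column open: eyes only partly assessable at month 6 with no criteria met in the visible part. The text below the table says these "may be scored successes or failures depending on their baseline status".

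Two pieces of text then fill that column.

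- **Detailed rule** (the paragraph after the five principles for incompletely assessable eyes). For a field that cannot be assessed at any time, "the worst value seen until that time will be assigned for the unavailable measurement". There is no condition on baseline readability. The paragraph adds: "Decreasing ability to assess eyes which had signs of uveitis will imply failure of therapy".
- **Summary bullets** (end of 3.1, introduced as a brief summary of guiding principles). The first begins "For the primary outcome, if any portion of the eye cannot be assessed at baseline", requires that the portion still be unreadable at Visit 6 or 12, and concludes that "if all other markers of success are met, this portion of the eye would be considered to have had successful therapy". The second covers a portion that was completely assessable at baseline and is unreadable by Visit 6 or 12; "then the last worst observation for this eye would be carried forward and used at the assessment of this eye portion".

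Intermediate grades will exist: "active retinal/choroidal lesions will be measured at Baseline, Week 2, Month 1 and every subsequent 4 weeks until the 6 month assessment". Scoring is by patient, and both eyes must succeed.

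**The concern.** The detailed rule uses everything seen up to month 6. The first bullet, as worded, uses only the two end visits. Where a region is unreadable at both ends but was graded inflamed in between, they give opposite scores for the primary endpoint.

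No other provision settles the case. The second bullet does not reach a region that was unreadable at baseline. Mid-study inflammation does not decide the outcome by another route, because Protocol 2.5.2 states that "increase in inflammation early on in the trial is not an indication of treatment failure". The methods in SAP 3.5 are limited to loss to follow-up and dropout. The outcome of such a patient would therefore depend on which paragraph is programmed. Under the bullet, inflammation recorded on study drug would be followed by a score of success because the view was later lost, although the detailed text treats loss of view in an eye with signs of uveitis as failure. The same definition of success is used at the interim analyses, in the non-inferiority assessment and in Aim 2.

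**Working it through.** The plan states no figure on this point, so there is none to reproduce. The check applies both rules to every possible record.

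**Step 1. Enumerate.** Let a region be U (unreadable), 0 (controlled by Protocol Table 2) or 1 (not controlled) at baseline, at an intermediate visit and at month 6. Nine trajectories end in U. The score shown is for that region, with all other markers assumed met.

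| Baseline – intermediate – month 6 | Detailed rule | Summary bullets |
|---|---|---|
| U–U–U | no value to assign | success |
| U–0–U | success | success |
| **U–1–U** | **failure** | **success** |
| 0–U–U | success | success |
| 0–0–U | success | success |
| 0–1–U | failure | failure |
| 1–U–U | failure | failure |
| 1–0–U | failure | failure |
| 1–1–U | failure | failure |

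Seven trajectories agree. In U–U–U the bullet fills a real gap, because the detailed rule has nothing to carry forward. U–1–U is the only contradiction.

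The agreement in 1–0–U depends on reading the second bullet's carried value as the worst one seen. Its wording could also mean the latest. The detailed text points to worst: one of its accepted misclassifications is a lesion that resolved, was later hidden by cataract, and is scored a failure.

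**Step 2. Who can be affected.** Eligibility under SAP 3.1 requires one fully assessable eye that meets the severity criteria (type C). A region unreadable at baseline is therefore in the fellow eye, of type B or D.

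**Step 3. Scale.** SAP 3.4.1 plans 108 per arm with 10% lost: 108 × 0.90 = 97.2, so about 97 evaluable per arm and 194 in all. The documents give no frequency for U–1–U. The following inputs are assumptions:

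- 15–30% of patients have a region unreadable at baseline;
- 30% of those become readable and then unreadable again at month 6;
- 30–50% of those were inflamed while readable.

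Low end: 0.15 × 0.30 × 0.30 = 1.35%, and × 194 = 2.6 patients. High end: 0.30 × 0.30 × 0.50 = 4.5%, and × 194 = 8.7 patients.

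The patient's outcome changes only if everything else meets success, in both eyes. Taking the planning success rates of 40% and 60% as a rough proxy: 2.6 × 0.40 = 1.0 and 8.7 × 0.60 = 5.2, so about 1 to 5 patients across both arms.

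**Step 4. Effect on the comparison.** One patient moves an arm's success proportion by 1/97 = 1.03 points. The rule applies to both arms, so the difference moves by the excess of affected patients in one arm × 1.03. Five patients split 3 to 2 move it by 1.0 point. All five in one arm would move it by 5/97 = 5.2 points.

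**The case against.** The best defence is that *still* unreadable means unreadable throughout. Principle 4 of the same section supports this: treatment will not reverse the damage that hides parts of the eye, so baseline unreadability is treated as lasting. On that reading the first bullet covers only U–U–U and complements the detailed rule. It is a fair reading, but the SAP does not state it. The bullet names only baseline and Visit 6 or 12, and the scoring text points to baseline status, not to what was seen in between. The bullets call themselves a summary, which favours the detailed rule, but no order of precedence is given.

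Second, SAP 3.2.2 item 11 plans an alternative definition that scores any worsening of assessability as failure. That is a sensitivity analysis and does not fix the base rule. Unreadable at both ends is also arguably not a worsening.

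Third, a reader might infer a stronger problem: that the view clears on prednisone, is lost again as disease returns during the taper, and active disease is then routinely counted as success. The documents do not support this. Haze that blurs or hides the optic nerve head is itself graded 3+ or 4+ (Protocol 5.3.2), and control requires 0.5+ or less (Table 2). Such an eye would usually fail at month 6 under both rules. The obstruction that the protocol names as preventing a reliable haze grade is a dense or mature cataract, which would not be expected to clear and return, and surgery is not allowed during the study (Protocol 3.2.5). The remaining cases are few. This part of the objection stands and limits the size of the point.

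**Conclusion.** The inconsistency is real on the wording, and narrow. One of nine trajectories is scored in opposite ways, in a fellow eye only, and it matters only when all other markers and the other eye succeed. It is probably uncommon. The estimate of 1 to 5 patients rests wholly on the assumed inputs in the working, and the assumption that 30% regain and then lose the view sits uneasily with principle 4.

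A reader might take the 3 to 9 patients obtained before requiring overall success, place them in one arm and set the result against the 20-point target difference. That would overstate the effect: it omits a condition in the rule itself and treats a rule common to both arms as if it acted on one. Nor does the point show that the scoring of unreadable eyes is unsound in general, since the rules agree in seven trajectories and the bullet fills a gap in an eighth.

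It is still worth correcting. A primary-endpoint algorithm should give one answer per record, fixed before the data are seen, and the accepted misclassifications listed in SAP 3.1 do not include this case.

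**What to change.** In SAP 3.1:

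- Limit the first summary bullet to portions that could not be assessed at baseline or at any visit through month 6 (or month 12 for that endpoint). These are scored as successful if all other markers are met.
- Add that a portion graded at any visit takes the worst value seen, as in the detailed rule.
- In the second bullet, replace the last-worst wording with worst value seen.
- State that the detailed rule governs if it and the summary differ.

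This keeps the bullet's useful role for regions never read. The cost is a wording change and a small edit to the endpoint code, with no new data. The downside is that a few more patients may be scored as failures, which is in line with the conservative approach the SAP says it has chosen.

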3.1.1 Demographics and Patient History

All demographic and history variables (in particular, age, gender, occupation, and ethnicity/national origin) determined at enrollment will be summarized by counts and percentages tabulated by treatment assignment.

3.1.2 Prior and concurrent medication

We will present the oral and topical corticosteroid doses at presentation (specifically, the current daily dose at baseline) and other medications by randomization arm and study site.

3.1.3 Baseline comorbidities and history

Clinical variables at baseline (in particular, anatomical site and vasculitis) will be presented by gender, age, and study site. We will also tabulate the presence of associated systemic disease at baseline. Anatomical site will be classified at the patient level as site of most serious involvement. For example, if a patient has anterior inflammation in the right eye and panuveitis in the left, they would be classified as a panuveitis patient.

3.1.4 Compliance

Compliance is assessed through patient self-report and regular pill counts by study coordinators at each visit when patients bring in their medications.

3.2 Analysis

3.2.1 Summary of Principal Outcome Variables and Regression Variables

Variables

- Primary outcome: Patient treatment success by six months (see MOP, Section 2.6)
- Patient treatment success at twelve months (Phase I)
- Successful control of inflammation in both eyes by twelve months, with complete discontinuation of corticosteroids
- Best spectacle-corrected visual acuity, at baseline and at the time of failure or six months (two observations per patient)
- Time to corticosteroid sparing control of inflammation (6 months and 12 months)
- Change in health related quality of life subscores (PCS and MCS) from SF-36 and Vision Related Quality of Life from NEI-VFQ-25 and IND-VFQ at six months and twelve months

- Reason for discontinuation of therapy (if applicable) at six months and twelve months
- Macular thickness at baseline, and at six months and twelve months
- Presence of macular edema at six months and twelve months
- Vitreous haze assessed clinically by the NEI and Davis scales at baseline, six months, and twelve months
- Vitreous haze as assessed by the photographic grading of haze by the NEI and Davis scales at baseline six months and twelve months
- The proportion of patients discontinuing due to serious adverse events at six months and twelve months
- Tabulate the occurrence of dose reduction used in immunosuppressive treatment.
- Treatment efficacy of VKH patients at six months and twelve months
- Treatment efficacy of patients with vasculitis at enrollment

Note that the presence of cataracts renders assessment of vitreous haze more difficult. Vitreous haze measurements in the presence of certain cataracts will be considered less reliable, and this will be considered in statistical modeling. Analyses will be repeated for differing assumptions about this bias. A maximum likelihood latent variable model will be considered, in which a true underlying vitreous haze level predicts an observed value. The observation model will include a higher probability of yielding a large observed value in the presence of a cataract.

Major independent variable of interest

- Treatment assignment (methotrexate or mycophenolate mofetil)

Additional regression variables used in selected analyses

- Anatomic location (coded dichotomously as either intermediate (code 0) or as being either posterior uveitis or panuveitis (code 1))
- Country
- Study site
- Gender
- Age
- Baseline quality of life (health and vision related)
- Baseline best spectacle-corrected visual acuity, vitreous haze, macular thickness
- Vasculitis

Inclusion of Data

- Data will be included for all outcomes within the window period of -2 weeks to +4 weeks around the 6 Month Visit date for Phase I (0-6 months).
- Data will be included for all outcomes within the window period of -2 weeks to +4 weeks around the 12 Month Visit date for Phase I (6-12 months).
- Data will be included for all outcomes within the window period of -2 weeks to +4 weeks around the 6 Month Visit for Phase II (0-6 months).

3.2.2 Specific Aim 1

Primary Analysis.

The primary analysis will be a logistic regression model, predicting treatment success at 6 months based on treatment arm. We wish to aggregate sites within countries, and countries within treatments provided we find no evidence of heterogeneity of sites or countries.

Specifically, the pre-specified primary analysis will be performed as follows. We denote the assignment group of patient i , $i=1, \dots, N$ (where N is the number of subjects) by X_p^1 which equals 0 when the patient is in the methotrexate group and 1 when the patient is in the mycophenolate mofetil group. The outcome variable is Y_p which is 1 if treatment success of patient i is achieved by six months, and 0 otherwise. The variable is missing if the patient is lost to follow-up or drops out of the study for reasons other than discontinuation due to intolerance or adverse events; if the patient discontinues the medication due to intolerance or adverse events such as abnormal laboratory findings, the value is 0.

The primary analysis is a logistic regression with treatment arm as a predictor. For the primary analysis, we propose to use study site as a *random effect* (random intercept model). The null hypothesis is that the regression coefficient for treatment arm equals zero, which will be tested using a likelihood ratio test with one degree of freedom. We will also fit the following models: (a) a model including drug, site, and drug \times site interaction, (b) a model including only drug and site, (c) a model including only drug and country, and (d) a model with drug, country, drug-country interaction, and site within country. Countries or sites with fewer than three observations will be pooled together. Provided there is no evidence of treatment \times site interaction or treatment \times country interaction, we will report pooled treatment effects and confidence intervals. In the event evidence suggests a difference between treatment sites, we will report treatment effects by site, and repeat the analysis excluding particular sites. Similarly, evidence of a treatment \times country interaction will lead us to report treatment effects and confidence intervals by country.

Simulations suggest that use of a model containing interaction terms between site or country and treatment for the primary analysis is undesirable. Such a procedure results in modest loss of power unless the treatment effect is of opposite sign in different sites or countries.

The hypothesis test is to be two-sided with alpha of 0.05. We propose to compute the P-value by permutation testing, based on the block randomization scheme.

Prespecified Subgroup Analysis.

The prespecified subgroup analysis will test the hypothesis that there is a treatment effect separately in each anatomic group, using a logistic regression model.

We denote the two anatomic groups by X_i^3 , which equals 0 when the patient is in the intermediate group and 1 when the patient is in the posterior/pan group. In the intermediate subgroup, we plan to determine whether there is evidence of a treatment effect (regardless of the effect in the posterior/pan group). Specifically, we will conduct this analysis in two ways: anatomical site at enrollment (split into three categories: anterior, anterior/intermediate or intermediate only, and posterior/panuveitis), and anatomical location by history (split into two

categories: anterior/intermediate or intermediate only, and posterior/panuveitis). Anatomical location by history is considered the prespecified analysis; anatomical location at enrollment will supplement this finding.

We propose to proceed as follows. We propose to begin with Equation (1), adding terms $\beta_3 X_i^3 + \beta_{13} X_i^1 X_i^3$ for anatomic location and for treatment-location interaction. We wish to test the hypothesis that $\beta_{13} = 0$, i.e. that there is a difference in treatment efficacy between the anatomic locations, controlling for country. Alternative models will be fit in which the country, site, and treatment x country terms are omitted.

We will also report relative risks in each substratum, using relative risk regression.

Additional analyses will add gender and age to the predictors. The entire analysis will be repeated for each gender, and separately for each country (US and India) and anatomic location.

Planned Secondary Analyses.

Each of the following secondary analyses is designed to test the hypothesis that treatment assignment affects a given outcome, after controlling for selected covariates. All analyses will be repeated without controlling for covariates (i.e., using treatment assignment as the only predictor). In all cases, appropriate regression diagnostics and/or goodness of fit tests will be performed (further details are given below). In addition, we will compute jackknife influence statistics in each analysis, to determine whether or not any single observation (eyes or patients, as appropriate) have an undue effect on the final conclusion. All models with site effects will be repeated omitting this effect, and again repeated including a treatment-site effect, and with country and/or treatment by country interactions (i.e., pooling within countries when appropriate). When reporting findings, care will be taken to distinguish the single prespecified test from supplemental tests (whether prespecified or unprespecified); exploratory analyses will always be labeled as such. All alpha levels are to be two-sided.

1. *Twelve-month endpoint for successes.* We propose to compare the proportion who maintain successful control for twelve months (i.e. the outcome is the proportion who have achieved control in all study eyes both at the six month visit and at the 12 month visit) between the two study arms. Per protocol, patients with successful control of their inflammation at 6 months remain on the same treatment until 12 months. We will use the same statistical model (and Wald procedure) as for the primary analysis. We test the hypothesis that the coefficients for treatment assignment and treatment assignment/anatomic location interaction both equal zero.

2. *Time to corticosteroid sparing control of inflammation.* We propose to use a Cox proportional hazard model with the outcome being the time to (1) first steroid-sparing control, and separately (2) first control of inflammation, with treatment assignment (and interaction) as the predictors. Time to first steroid-sparing control is the principal prespecified analysis here; alternative approaches will be conducted for additional insight and as sensitivity analyses. We will supplement this analysis with a parametric survival analysis using the Weibull distribution and also with a gamma distribution (note that individuals may drop out at any time, not just at the monthly visits), and with a method treating the time to success as interval censored. The outcome for this analysis is a single number for each patient (not for each eye). The primary statistical

result will be the Wald test for the treatment assignment coefficient. We will repeat the analysis using study site as a fixed effect in this model (and as a sensitivity analysis, will explore random-effects survival analytic methods which are becoming available, see Pankratz et al.).⁶ In supplementary analyses we will include age and anatomic location as additional covariates.

3. *Country and site within country.* We denote the country by X_i^2 , which will be 0 for US locations and 1 for Indian locations; X_n^4 is 1 only for patients in the second Indian site and 0 otherwise, while X_{iz}^4 is 1 only for patients in the second US site and 0 otherwise. As mentioned under the Primary analysis, we propose to fit models with country only, drug by country interaction, and with a drug by country interaction, including site within country as well. Analysis will be conducted within each site, then pooling the sites within country together. Further details regarding pooling across centers are provided above under the main prespecified analysis.

4. *Best spectacle-corrected visual acuity (BSCVA).* The primary outcome variable for this secondary outcome will be the change in best spectacle-corrected visual acuity from baseline to final (as defined in the FAST MOP, i.e. for those who successfully control inflammation as defined in the MOP, or at the time of failure for those who fail; MOP, Section 2.6). Visual acuity change scores are available for both eyes for each patient.

The primary analysis will use a linear mixed-effects regression, where the outcome variable is the change in BSCVA in each eye, using treatment assignment as a statistical predictor (regressor, independent variable); a random effect will be used at the individual level, because of the possibility that changes in the two eyes from a given patient are correlated. In a supplementary analysis, we will include as predictors (independent variables) anatomic location of uveitis, interaction between anatomic location and treatment assignment, and the study site, together with a random effects for patient. We will fit these models using maximum likelihood (R procedure `lmer`) and use likelihood-ratio tests to test the hypothesis that treatment assignment affects BSCVA change. Only eyes that are eligible and meet inflammation criteria at baseline will be included in this analysis. If at a given visit, vision cannot be assessed, we will carry the last observation forward. Additional sensitivity analyses for missing data will be used (including mixed effects models controlling for time, including all data from an individual).

Also, if there is no eye at Month 6 to assess, the patient will be given a logMAR value of 2.0.

Because of the possibility that the outcome variable (BSCVA change score) will exhibit non-normality, we will repeat the analyses using transformations of the outcome data (including power and log transformations, or more general monotone transformations).

Additional analyses will be performed using age, gender, ethnicity, and the steroid dose at each month as predictors.

An additional supplemental analysis will be conducted using final BSCVA (instead of the change score) as the outcome, and including baseline BSCVA in each eye as a predictor, using methods otherwise identical to those above.

5. *Quality of life.* We will also use a linear mixed model to assess health-related quality of life, measured by the SF-36 questionnaire (PCS and MCS scores) and vision related quality of life NEI-VFQ-25 and IND-VFQ at 6 months or at the time of failure, as described in the Manual

of Operations. Predictors will be baseline quality of life, age, gender, ethnicity, study site (as a random effect), and treatment assignment, and we will test the hypothesis that the regression coefficient corresponding to treatment assignment equals zero using the Wald t-test. Similar assessments will be performed for vision-related quality of life questionnaires.

6. *Reason for discontinuation.* Individuals who discontinue study medication may do so due to inability to tolerate side effects, due to lack of efficacy, or for safety reasons. The outcome variable is whether the person discontinued due to intolerance, discontinued due to lack of efficacy, discontinued due to safety, or did not discontinue the medication. Because study site may be an important factor, we will use polytomous regression to model the discontinuation result as a function of treatment assignment (using a fixed effect for study site).⁷ If evidence is found that treatment assignment influences discontinuation result, further analyses may be conducted to determine whether or not treatment assignment is associated with discontinuation due to intolerance, lack of efficacy, or to safety, or some combination of these. We propose to classify all individuals in a two by four table according to treatment assignment and discontinuation (not discontinued, discontinued due to intolerance, discontinued due to lack of efficacy, discontinued due to safety) and conduct the Fisher's exact test (in its $r \times c$ form). The use of an overall test prior to further analysis is designed to protect the overall error rate.

